The DCS will follow patients for 12 months, while monitoring response.¹⁵⁸ At the start, the DCS will attempt to have telephone sessions or contacts at least every 2 weeks. For patients who achieve remission ($\geq 50\%$ PHQ-9 reduction and < 3 MDD symptoms³⁶), the DCS will develop a relapse prevention plan and follow up monthly. Step 2 treatment – which involves either augmenting Step 1 treatment with an antidepressant or psychotherapy or switching to another antidepressant or psychotherapy – will be delivered to patients who do not achieve remission. If a patient does not respond after 6-10 more weeks, Step 3 treatment will be initiated, which consists of additional medications and psychotherapy, hospitalization, or other services. In the IMPACT trial,³⁶ intervention patients had 9.2 ± 6.2 in-clinic sessions and 6.1 ± 5.1 telephone contacts with a DCS during the 12 months of treatment. At the end of the 12 month treatment phase, the participant will receive a certificate indicating completion of eIMPACT treatment. We expect similar numbers in our trial, although most sessions/contacts will be via telephone. Based on our experiences, one DCS can manage 80-100 patients. The maximum number of patients in treatment at any given time in this trial will not exceed 80.

Usual Care

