For Usual Care patients who score in the "severe depression" range (20-27) on the PHQ-9 at the mid-treatment (6 months), the DCS (a) will contact the patient's primary care provider in person, by phone, or through the electronic medical record to notify the provider of the patient's high depressive symptoms and to urge the provider to follow-up and (b) will provide a list of local mental health services, including referral to a psychiatrist outside of the study team. In addition, participants in both treatment groups who continue to exhibit

elevated depressive symptoms (PHQ-9 ≥ 10) at post-treatment will be urged to follow-up with their primary care providers regarding their depression. Their providers will also receive a letter from the study team indicating that their patient has completed participation in the treatment phase of the trial and continues to have elevated depressive symptoms. This letter will also urge physicians to follow-up with their patients and will provide a list of local mental health services. Finally, for participants in both treatment groups who score in the “severe depression” range (20-27) on the PHQ-9 during an annual follow-up call, the DCS (a) will contact the patient’s primary care provider in person, by phone, or through the electronic medical record to notify the provider of the patient’s high depressive symptoms and to urge the provider to follow-up and (b) will provide a list of local mental health services, including referral to a psychiatrist outside of the study team.

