8.0 Statistical Considerations

Sample Size and Power Considerations

Endothelial Dysfunction

Using the effect size of depression treatment on FMD from our pilot trial, we need 88 patients (44 per arm) to detect a group difference in FMD of 1.7% ($d = 0.61$) at 12 months, assuming a power level of 0.80 and a Type I error of 0.05. This would be a clinically relevant difference. Assuming a conservative attrition rate of 20%,²⁰⁴ we will have 172 completers ($220 \times .80$) for FMD, yielding power levels of 0.98 for $d = 0.61$ and 0.80 for $d = 0.43$.

Candidate Mechanisms

We expect at a power level ≥ 0.80 for the candidate mechanisms (Hypotheses 2-5), as we will be able to detect effect sizes as small as $d = 0.43$ with 172 completers. In our IMPACT study³⁵ and pilot trial, effect sizes for depressive symptoms ($d = 0.69$ and 1.33), IL-6 ($d = 0.43$), and CRP ($d = 0.78$) were in the medium-to-large range. In other studies, effect sizes of 0.52 were found for psychological interventions on heart rate variability,²⁰⁵⁻²⁰⁷ 1.00 for SSRIs on IL-6,¹⁴³ 0.74 for SSRIs¹⁴³ and 0.85 for CBT¹³⁸ on CRP, 0.91¹⁴⁶ and 0.46¹⁴⁴ for SSRIs on BTG, and 0.87 for SSRIs on PF4.¹⁴⁴

CVD Events

Over the mean observation period of 4 years, we anticipate a cumulative CVD event rate of 20% (39 events) and a 25% lower relative risk ($HR \leq 0.75$) in eIMPACT versus usual care. These estimates are reasonable, as we observed a CVD event rate of 24% and a 46% lower relative risk (event rate: 18% vs. 31%) in our IMPACT secondary analysis that had a 4-year observation period. Our high-risk sample will differ from the typical sample of a risk reduction trial in that (a) all patients will have depression and ≥ 1 CVD risk factor and (b) many will be of low SES and/or African American, two groups at elevated risk for CVD event.^{1,171} Although we expect to have CVD event data for nearly all patients, we assume a conservative attrition rate of 10%, leaving 194 completers. As is typical of Phase 2 trials, our trial is not designed to detect a statistically significant difference in clinical events; however, a 25% relative risk reduction would be a clinically relevant signal (statin therapy reduces risk by $\approx 30\%$ ¹⁵⁶) and has been used to power recent event-driven Phase 3 cardiology trials.¹⁵⁷

Statistical Analyses

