We will use the intent-to-treat approach.²⁰⁸ All tests will be two-tailed with $p < .05$ considered significant. Supplemental analyses of completers will be performed. We will assess for differences in all baseline factors. Due to randomization, we do not expect baseline group differences. Even so, any differences will be taken into account when interpreting results, and any baseline factors that differ between the groups will be included as covariates in sensitivity analyses. Aim 1: We will test our hypothesis that eIMPACT patients will exhibit greater improvement in endothelial dysfunction (Hypothesis 1) by performing a two-sample t-test with FMD at 12 months as the dependent variable. If there is a group difference in baseline FMD, analyses of covariance (ANCOVAs) adjusting for baseline level will also be performed. We will also explore whether eIMPACT patients show a clinically relevant reduction (25% lower relative risk) in CVD events by running a Cox proportional hazards model with treatment group predicting time to first CVD event. Patients will be censored at non-CVD death or the end date. We expect to observe a $HR \leq 0.75$. Aim 2: We will test our hypotheses that eIMPACT patients will exhibit greater decreases in the candidate mechanisms (Hypotheses 2-5) by performing two-sample t-tests with SCL-20 score, high-frequency heart rate variability, IL-6, CRP, BTG, and PF4 at 12 months as the dependent variables. If baseline group differences are found, ANCOVAs adjusting for baseline level will

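### The primary analysis is declared intent-to-treat but rests on an unadjusted t-test with no stated method for missing 12-month FMD; baseline adjustment should be unconditional and paired with a stated missing-data method

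*Combined protocol and SAP*

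**What the plan says.** Section 8.0 (Statistical Analyses) sets the principle, "We will use the intent-to-treat approach", and adds "Supplemental analyses of completers will be performed". Hypothesis 1 is tested by "performing a two-sample t-test with FMD at 12 months as the dependent variable". On baseline FMD the plan says: "If there is a group difference in baseline FMD, analyses of covariance (ANCOVAs) adjusting for baseline level will also be performed". Other baseline factors that differ between the groups enter sensitivity analyses only. The outcomes for Hypotheses 2-5 are handled in the same way: t-tests at 12 months, with ANCOVA added if baselines differ.

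Section 8.0 (Sample Size and Power Considerations) introduces the loss with "Assuming a conservative attrition rate of 20" percent and concludes "we will have 172 completers" for FMD.

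Section 5.0 schedules FMD in person at the pre-treatment and 12-month visits only. There is no 6-month FMD, although depressive symptoms and behavioural factors are collected at 6 months. Randomisation follows the pre-treatment visit, so baseline FMD is scheduled for every randomised patient.

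No section names imputation, a likelihood-based method, weighting or a sensitivity analysis for missing 12-month FMD.

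**The concern.** A t-test on a single 12-month value cannot include a patient who lacks that value. The declared principle covers everyone randomised, but the named test does not say how to reach them. Up to a fifth of patients could therefore be dropped by default or handled by a method chosen after the data are seen.

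The one tool in the plan that would help, adjustment for baseline FMD, depends on the wrong condition. Randomisation balances baseline FMD among all randomised patients, so a baseline comparison there says nothing about whether later loss was uneven. The condition also gives up precision in most trials.

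FMD is the sole primary outcome, and a positive result is meant to justify a Phase 3 trial. A moderate difference, near 1% FMD, is the kind of result that uneven loss could push across the significance line.

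**Working it through.** **Inputs from section 8.0.** 220 randomised; 20% attrition; 172 completers; difference 1.7% FMD at d = 0.61; two-sided alpha 0.05. Implied SD = 1.7/0.61 = 2.79% FMD.

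**The plan's own figures.** Noncentral-t power with 86 per arm is 0.978 at d = 0.61 and 0.801 at d = 0.43, matching the printed 0.98 and 0.80. With 110 per arm it would be 0.995 and 0.888. The printed power therefore counts only patients with FMD. (220 x 0.80 is 176, not 172; this changes power by under one point.) Expected loss is 220 x 0.20 = 44, or 220 - 172 = 48.

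**Smallest significant difference.** t(.975, 174) x 2.79 x sqrt(4/176) = 0.83% FMD.

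**Bias of the t-test.** Bias = difference between arms in (share missing x deficit of the missing). The 0.5 SD (1.4% FMD) deficit and the loss splits are assumptions; no document gives them.

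| Loss by arm | Bias | False-positive rate |
|---|---|---|
| 20/20, same deficit | 0 | 5.0% |
| 22/18 | 0.04 x 0.5 SD = 0.06% | 5.2% |
| 25/15 | 0.10 x 0.5 SD = 0.14% | 6.3% |
| 30/10 | 0.20 x 0.5 SD = 0.28% | 10.0% |

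**How often the condition is met.** Suppose a group difference means p < .05. Compared in all randomised patients, it is met in about 5% of trials (simulated 5.2% at 25/15 and 4.4% at 30/10). Compared only in patients with 12-month FMD, with loss driven by baseline FMD, it is met in 12% and 28%.

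**Unconditional ANCOVA, loss driven by baseline FMD.** Simulated with no true effect, 110 per arm and an assumed baseline correlation of 0.5. At 25/15 and 30/10 the t-test bias is 0.14% and 0.27%, with rejection 6.5% and 9.9%. The ANCOVA bias is 0.00% in both, with rejection 4.6% and 5.3%.

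**Where ANCOVA does not help.** A second simulation assumed 20% loss per arm, related to the driver in eIMPACT and random in usual care, with correlations of 0.3 to 0.7:

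- Loss driven by another baseline factor: bias about 0.15% before and after adjustment.
- Loss driven by a post-baseline factor: 0.16-0.22% before and after.
- Loss driven by 12-month FMD itself: 0.48-0.50% falls only to 0.25-0.45%.

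**Precision.** With equal baselines the width ratio is sqrt(1 - r^2): 0.95, 0.87 and 0.71 at r = 0.3, 0.5 and 0.7. Allowing for loss, simulation gives about 0.97, 0.88 and 0.73. The plan gives no 12-month correlation; its FMD repeatability of 0.70 is over 1-4 weeks in 11 healthy volunteers.

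**Tipping shift for the t-test at 20% missing.** Shift = (observed - 0.829)/0.20. An observed 1.0% tips at 0.85%, 1.2% at 1.85% and 1.7% at 4.35%. A shift capped at 1.7% moves the estimate by 0.20 x 1.7 = 0.34%, so it can show a crossing only up to 0.829 + 0.34 = 1.17%. With ANCOVA at width 0.88, the threshold is 0.829 x 0.88 = 0.73%, and an observed 1.0% tips at (1.0 - 0.73)/0.20 = 1.35%.

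**The case against.** The plan lists completer analyses as supplemental, so its authors evidently intend the main analysis to differ. Powering on expected completers is ordinary caution and is compatible with imputation. This stands: a reader might infer that the plan has mislabelled an observed-case analysis as intent-to-treat, but the documents do not say so. They leave the main analysis under-specified, with observed cases as the default.

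A reader might also infer that a completer means someone who finished treatment, from "the participant will receive a certificate indicating completion of eIMPACT treatment" in section 5.0 or "completed participation in the treatment phase of the trial" in section 7.0. Neither passage uses the word. The second covers both arms, and section 8.0 itself uses completers for patients with outcome data. Nothing here rests on that reading.

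The harm depends on assumed uneven loss. Withdrawal for serious illness (section 7.0) applies to both arms. The plan also works at retention: a pre-randomisation visit as a compliance screen, payment and transport for the 12-month visit, a 6-month call to everyone, and 6-monthly board reports on retention. At 22/18 the effect is negligible. Against this, staff contact during treatment differs by arm, and one withdrawal route depends on the eIMPACT psychiatrist's assessment. Uneven loss is therefore possible, in either direction. The documents do not support the inference that the trial is biased towards eIMPACT.

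Finally, ANCOVA also drops patients without 12-month FMD. That is correct, and it is why ANCOVA alone is not enough.

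**Conclusion.** The omission is plain from the text: intent-to-treat is declared, the primary test is unadjusted and by default uses observed cases, no method for missing FMD is named, and baseline adjustment is conditional and secondary. Making the ANCOVA primary is better whether or not loss is uneven, because it narrows the interval by roughly 3%, 12% or 27% at assumed correlations of 0.3, 0.5 or 0.7. It also removes bias from loss explained by baseline FMD, under a linear model.

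The size of any bias is not established. It is zero when loss is alike in both arms. At the assumed 0.5 SD deficit it is 0.06% to 0.28% FMD across the splits shown. A result near 1% could be affected. A pilot-sized 1.7% would need the missing patients in one arm to be over 4% FMD worse than assumed, which is far beyond these scenarios. This should be fixed. Confidence is high for the omission and the precision gain only.

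**What to change.** In section 8.0:

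1. Make the ANCOVA on baseline FMD the unconditional primary model for Hypothesis 1, and do the same for Hypotheses 2-5 with their own baseline values. Keep the unadjusted t-test as supplemental.
2. To cover all randomised patients, multiply impute missing 12-month FMD within arm from baseline FMD, sex, age group and other collected data such as 6-month scores. Analyse with the same ANCOVA, combine by Rubin's rules and state the missing-at-random assumption. The gain over step 1 comes from predictors beyond baseline FMD.
3. Add a delta-adjusted sensitivity analysis on that model. Shift missing values in each arm separately until significance is lost, without capping the range at 1.7%. Report missing FMD by arm and reason.

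The cost is SAP wording and modest programming, with no new data or visits. It should be settled before 12-month FMD is compared by arm. Imputation from baseline FMD followed by a t-test gave intervals 0.99-1.04 times the plan's width. Imputation followed by ANCOVA, and the added predictors, were not simulated. Neither step corrects loss that the collected data do not predict; step 3 shows how much of that the result can bear.

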Patients will undergo FMD assessments at [name] laboratory in accordance with consensus guidelines.⁸¹ [name] as well as [name] and [name] (our vascular ultrasonographers) have undergone certified training through the University of Wisconsin Brachial Artery Reactivity Testing Symposium. Our group has performed 700+ FMD assessments in the past 10 years. We utilize a GE Logiq E ultrasound system with AccessPoint 2011 software. To illustrate the reproducibility of our results, we performed paired FMDs over 1-4 weeks in 11 healthy volunteers in 2013. Intraclass correlations for baseline diameter, reactive hyperemia, and FMD were 0.98, 0.98, and 0.70, which compare favorably to other laboratories.¹⁸¹⁻¹⁸³

After a 10-minute supine rest, high-resolution baseline images of the brachial artery will be obtained from 3 consecutive cardiac cycles. Next, the forearm cuff will be inflated to 250 mmHg for 5 minutes and then rapidly deflated. At 60 and 90 seconds post deflation, images from 3 consecutive cardiac cycles will be acquired. Brachial diameters will be measured at peak R wave. FMD values will be computed as % increase in diameter at 60 or 90 seconds post deflation^{196,197} (the larger of the two values). Percent change in reactive hyperemic flow velocities will also be computed to ensure that sufficient shear stress triggers were induced.

Atherogenic Physiologic Factors (Secondary Outcomes)

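### The test of Hypothesis 1 ignores baseline FMD unless the arms happen to differ on it; unconditional ANCOVA would be more precise at almost no cost

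*Combined protocol and SAP*

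**What the plan says.** Section 8.0, Statistical Analyses, tests Hypothesis 1 by "performing a two-sample t-test with FMD at 12 months as the dependent variable. If there is a group difference in baseline FMD", an ANCOVA on the baseline level is run in addition. Baseline therefore enters only conditionally. Aim 2 is handled in the same way, by "performing two-sample t-tests with SCL-20 score, high-frequency heart rate variability, IL-6, CRP, BTG, and PF4 at 12 months as the dependent variables", again with ANCOVA added only when baseline differs.

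No criterion is attached to a baseline difference in FMD. The section's general two-sided .05 level may be what is meant. The section does not say which result governs if the two analyses disagree. It does say that "any baseline factors that differ between the groups will be included as covariates in sensitivity analyses", so the best reading is that the t-test decides and ANCOVA is supportive.

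Section 5.0 schedules FMD at the pre-treatment visit, before randomisation. Section 4.0 randomises only patients who attend that visit.

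**The concern.** Whether to adjust for baseline should depend on how well baseline predicts the outcome, not on whether the arms differ by chance. The plan expects no baseline differences, so it expects to leave baseline FMD out of its main test. Two things are lost:

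- **Precision.** The treatment estimate has a wider confidence interval than the collected data allow. This matters most for effects near the smallest the plan says it can detect.
- **Calibration under imbalance.** If the arms do differ at baseline, the deciding t-test carries that difference into the result, while the better-calibrated ANCOVA is only supportive.

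**Working it through.** **Inputs from the documents.** Section 8.0: two-sided alpha 0.05; planned FMD difference 1.7 points, d = 0.61; 172 completers, taken as n = 86 per arm; stated power 0.98 at d = 0.61 and 0.80 at d = 0.43. The implied SD is 1.7 / 0.61 = 2.79 points.

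**Assumed input.** The baseline-to-12-month correlation r is not given. The nearest figure is in Section 5.0: "Intraclass correlations for baseline diameter, reactive hyperemia, and FMD were 0.98, 0.98, and 0.70". Those are repeat scans 1-4 weeks apart in 11 healthy volunteers, so the 12-month value in this population may well be lower. I use r = 0.3 to 0.6 as the working range and show 0.1 and 0.2 as a check. Nothing comparable is given for the Aim 2 outcomes.

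**Step 1: reproduce the plan.** Power is taken from the noncentral t with 2n - 2 = 170 df and noncentrality d × sqrt(n/2), where sqrt(43) = 6.557.
- d = 0.61: noncentrality 4.00, power 0.978 (plan 0.98).
- d = 0.43: noncentrality 2.82, power 0.801 (plan 0.80).
- 44 per arm at d = 0.61: power 0.808, matching the plan's 88 patients.

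**Step 2: ANCOVA on baseline.** Residual variance is multiplied by 1 - r², so the noncentrality becomes d × sqrt(n/2) / sqrt(1 - r²), with 169 df. For example, at r = 0.5 and d = 0.43 it is 2.82 / 0.866 = 3.26. The equivalent sample size is 172 / (1 - r²).

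| Analysis | 1 - r² | Power, d = 0.43 | Power, d = 0.61 | FMD difference detectable at 80% power (points) | Equivalent N by t-test |
|---|---|---|---|---|---|
| t-test | - | 0.801 | 0.978 | 1.20 | 172 |
| ANCOVA, r = 0.1 | 0.99 | 0.804 | 0.979 | 1.19 | 174 |
| ANCOVA, r = 0.2 | 0.96 | 0.816 | 0.982 | 1.17 | 179 |
| ANCOVA, r = 0.3 | 0.91 | 0.836 | 0.986 | 1.14 | 189 |
| ANCOVA, r = 0.4 | 0.84 | 0.864 | 0.991 | 1.10 | 205 |
| ANCOVA, r = 0.5 | 0.75 | 0.899 | 0.996 | 1.04 | 229 |
| ANCOVA, r = 0.6 | 0.64 | 0.939 | 0.999 | 0.96 | 269 |

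At r = 0 ANCOVA power at d = 0.43 is still 0.801, so the lost degree of freedom costs nothing visible.

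**Step 3: does the conditional rule recover the gain?** Hardly. In 40,000 simulated trials at r = 0.5 and d = 0.43, with baseline p < .05 as the trigger, power was 0.80 for the t-test, 0.81 if either test may count once triggered, and 0.90 for ANCOVA always.

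**Step 4: calibration when baseline differs.** Under the null, the standardised baseline and outcome differences are approximately bivariate normal with correlation r. The chance that the t-test rejects, given baseline p < .05, is 0.098, 0.135, 0.185 and 0.249 for r = 0.3, 0.4, 0.5 and 0.6. Simulation (210,000 null trials per r) gave 0.096 to 0.247 for the t-test and 0.048 to 0.053 for ANCOVA in the same imbalanced trials. Over all trials the t-test rejected in 0.049 to 0.050.

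**Step 5: how often this changes a verdict.** Baseline p < .05 together with conflicting t-test and ANCOVA results occurred in 0.9-1.9% of simulated trials at d = 0.43 and 0.2-0.5% at d = 0.61.

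**Check on the completer count.** 220 × 0.80 is 176, not 172. With 176, t-test power at d = 0.43 is 0.810, and the conclusion is unchanged.

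**The case against.** The t-test is valid, the trial was sized on the unadjusted comparison, and its power figures reproduce. At the planned FMD effect, power is already 0.98. The value d = 0.43 is a detectability floor, not the planned effect, and most other effect sizes quoted in Section 8.0 are larger. At 0.52 for heart rate variability, for instance, t-test power is 0.92, and another study cited there puts IL-6 at 1.00. The size of the gain rests on an assumed correlation. For IL-6, CRP, BTG and PF4 no transformation is stated, so a linear-normal calculation may not carry over. The high conditional error applies to about 5% of trials, which are the ones where the plan would also run ANCOVA. The general .05 level arguably supplies the missing trigger.

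Much of this stands as a limit on size. The gain for FMD at d = 0.61 is small. At r = 0.1-0.2 the gain at d = 0.43 is under two points. Conflicting verdicts are rare, and the Aim 2 gains are less certain than those for FMD.

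It does not defend the rule. The plan itself relies on the floor for Hypotheses 2-5, "as we will be able to detect effect sizes as small as $d = 0.43$ with 172 completers", and its own earlier data put one outcome exactly there: "IL-6 ($d = 0.43$), and CRP ($d = 0.78$) were in the medium-to-large range". The lower BTG value it cites, 0.46, gives t-test power of only 0.85. Reading the trigger as p < .05 is what the calculations above assume, and it leaves adjustment tied to chance imbalance.

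**Conclusion.** The concern holds, as an efficiency improvement the plan should make rather than a flaw that invalidates the trial. With 172 completers and an assumed r of 0.3-0.6, unconditional ANCOVA adds about 4 to 14 points of power at d = 0.43 and 1 to 2 points at d = 0.61. It gives the precision of 189 to 269 patients analysed by t-test. Confidence in the direction is high; the size depends on r, which the documents do not give, and on approximately normal, linear data. Poor calibration of the t-test under baseline imbalance is a secondary argument, because it affects few trials.

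**What to change.** Make ANCOVA of 12-month FMD on treatment group and baseline FMD the single pre-specified test of Hypothesis 1, whatever the observed baseline difference. Do the same for each Aim 2 outcome with its own baseline value. Delete the baseline-difference trigger and keep the unadjusted t-tests as sensitivity analyses.

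Two refinements are worth writing in at the same time. Add sex and age group to the model, since randomisation is stratified on them. State how an unusable baseline measurement will be handled, since attending the visit does not guarantee a readable scan.

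The cost is a change of SAP wording. The baseline assessments are already scheduled, and the baseline covariate uses one degree of freedom per model (the two strata would use two more).

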At the end of the pre-treatment visit described below, the randomization procedure will be initiated. To balance the groups on two strong FMD correlates,⁹¹ randomization will be stratified by sex and age (50-59 and 60+ years) using random number sequences.¹⁶⁸ Sequentially numbered sealed envelopes containing group assignment will be prepared by the study statistician ([name]).

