This arm was modeled after the IMPACT trial control group.³⁶ At the pre-treatment visit, patients will be informed of their depression diagnosis and group assignment, will be provided with a list of local mental health services (with contact information) available to Eskenazi patients, and will be encouraged to follow-up with their primary care provider regarding their depression. These patients will also be reminded (from the informed consent statement) that, although we will pass along information to their primary care provider, participants in this group do not receive any depression treatment from the study team; instead, all depression treatments that participants in this group receive during the study are delivered by their usual providers. The patient's PCP will also receive a letter indicating that their patient has a depressive disorder and was randomized to usual care. This letter will encourage the PCP to follow-up with their patient to address their depression, will note that there are no restrictions on the care that these patients can receive, and will provide the same list of Eskenazi mental health services given to patients. Although this feedback could result in treatment that would not have occurred naturally in primary care, informational support alone is unlikely to improve depression outcomes.¹⁸⁰ Moreover, our pilot trial indicates that depression outcomes achieved with usual care in targeted clinics remain suboptimal (see c2.2). Patients in both arms will continue to have access to services that are part of usual care in the targeted systems. There will be no restrictions on the care received, although new depression treatments received outside of the trial are discouraged in the eIMPACT group.

Assessments

Revision Date: July 13, 2018

	Pre-Treatment* (0 months)	Mid-Treatment† (6 months)	Post-Treatment* (12 months)	Annual Calls‡ (2-4 calls)
Endothelial Dysfunction (Primary Outcome)	X		X	
Atherogenic Physiologic Factors (Secondary Outcomes)	X		X	
Depressive Symptoms (Secondary Outcome)	X	X	X	X
CVD Events (Exploratory Outcome)		X	X	X
Atherogenic Behavioral Factors	X	X	X	X
Conventional CVD Risk Factors	X		X	
Miscellaneous Factors	X	X	X	X

*Clinical Research Center Visit. †Telephone Call.

Endothelial Dysfunction (Primary Outcome)

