7.0 Study Withdrawal/Discontinuation

All participants will be considered enrolled at the end of the ResNet interview. The informed consent statement describes the possibility of and the procedures for withdrawing from the study. A participant may notify either the principal investigator or any member of the research team at any time via email, phone, or in-person that s/he wants to withdraw from the study for any reason. The schedule of participant reimbursement is as follows: \$100 for the pre-treatment visit, \$25 for the mid-treatment call, \$100 for the post-treatment visit, \$20 for each of the annual follow-up calls, and up to \$10 per visit to cover parking or transportation costs. If a participant withdraws before the pre-treatment assessment visit, no payment will be provided.

Other reasons for study withdrawal/discontinuation are (a) the participant's primary care provider or another provider seeing the participant (e.g., a psychiatrist outside of the study team) no longer believes that his/her patient is appropriate for this trial after a triggering of the Suicidal Ideation Protection Protocol or any other reason, (b) the participant develops acute or serious illness that precludes completion of the main study visits within the allowed timeframes, and (c) the participant, in the assessment of the eIMPACT psychiatrist, exhibits evidence of a psychotic disorder or bipolar disorder (both of which are exclusionary conditions and could interfere with treatment delivery/effectiveness) during the 1-year treatment phase of the trial. In the case of situation (b), the patient will not complete any future study visits or calls. However, if the patient provides permission, electronic medical record data (e.g., incident CVD events) will still be obtained going forward, consistent with our Authorization Form. In the case of situation (c), patients with a psychotic disorder or bipolar disorder would likely benefit from psychotropic medications, such as antipsychotic medications or mood stabilizer, that are beyond what are provided in this trial.

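### The exploratory Cox analysis of CVD events has no censoring date for patients whose record access ends, and its model leaves out the randomisation factors

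*Combined protocol and SAP*

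**What the plan says.** Section 8.0 (Statistical Analyses, Aim 1) specifies "running a Cox proportional hazards model with treatment group predicting time to first CVD event", and then "Patients will be censored at non-CVD death or the end date". No other censoring point is named. The same section sets an intent-to-treat approach, with completer analyses as a supplement. Under CVD Events it states "we assume a conservative attrition rate of 10%, leaving 194 completers", while expecting event data for nearly everyone.

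Section 7.0 lists three grounds for discontinuation besides voluntary withdrawal. After ground (b), acute or serious illness, visits and calls stop, and "if the patient provides permission, electronic medical record data (e.g., incident CVD events) will still be obtained going forward". The section does not address record access after the other routes. It points to the consent statement and Authorization Form, which are not in the reviewed text and may cover it.

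Section 4.0 states that "randomization will be stratified by sex and age (50-59 and 60+ years"). Section 8.0 allows covariates only as follows: "any baseline factors that differ between the groups will be included as covariates in sensitivity analyses". It sets out to look for an HR of 0.75 or less but names no confidence interval for it.

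**The concern.** A time-to-event analysis needs an end-of-observation date for every patient. Where record access has been refused, events can no longer be seen, yet the stated rule offers only non-CVD death or the end date. Applied literally, it counts unobserved time as event-free follow-up. That lowers the reported event rate in any case, and it shifts the HR towards the arm that loses more patients. Section 1.0 says that the effect estimates, CVD events included, will help to justify and design a Phase 3 trial, so an understated rate has some consequence.

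Separately, the design balances on sex and age group but the Cox model ignores both. The covariate provision is triggered only by an observed baseline difference, which stratification makes unlikely for these two factors.

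**Working it through.** **The plan's own figure.** Section 8.0 gives a 20% cumulative rate and 194 patients: 0.20 × 194 = 38.8, or 39 events, as stated. (220 × 0.90 is 198 rather than 194; 198 × 0.20 = 39.6, so the event count barely changes.)

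**Precision with 39 events.** Assuming 1:1 allocation, SE(log HR) = 2/√39 = 0.320, and log 0.75 = −0.2877.
- 95% CI around 0.75: exp(−0.2877 ± 1.96 × 0.320) = 0.40 to 1.40; two-sided p = 0.37.
- Chance of HR ≤ 0.75 with no true effect: Φ(−0.2877/0.320) = Φ(−0.898) = 0.18.

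**Effect of the literal censoring rule.** From the plan: 20% at 4 years, and follow-up of 3 to 5 years (section 5.0). Assumed: constant hazard, uniform follow-up, no treatment effect, loss spread evenly over follow-up, and every loss split by arm, since the documents give none.
- Hazard: λ = −ln(0.80)/4 = 0.0558 per year.
- Event probability if fully observed, 1 − e^(−λC) averaged over follow-up C from 3 to 5 years: 0.1996.
- Probability of an observed event in a lost patient, 1 − (1 − e^(−λC))/(λC) averaged likewise: 0.1036.
- Equal 10% loss: 0.90 × 0.1996 + 0.10 × 0.1036 = 0.1900. The reported rate falls from 20.0% to 19.0%, and the HR stays at 1.00.
- 12% loss in eIMPACT and 8% in usual care: (0.88 × 0.1996 + 0.12 × 0.1036)/(0.92 × 0.1996 + 0.08 × 0.1036) = 0.1881/0.1919 = 0.980. Dividing by the slightly larger person-time credited to eIMPACT gives a rate ratio of 0.978.

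| Assumed loss, eIMPACT/usual care | HR when the truth is 1.00 | P(HR ≤ 0.75) |
|---|---|---|
| 10%/10% | 1.00 | 0.18 |
| 11%/9% | 0.99 | 0.19 |
| 3%/1% | 0.99 | 0.19 |
| 12%/8% | 0.98 | 0.20 |
| 8%/12% | 1.02 | 0.17 |

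**Where to put movers.** Patients who leave the coverage of the Indiana Network for Patient Care (INPC) also stop being observed, but the study knows only some of them. This was simulated with 1.5 million patients per arm, assuming 2 or 4 INPC encounters a year and 10% of non-movers unreachable. Suppose 10% are lost in each arm, with 80% of movers known in eIMPACT and 50% in usual care. Censoring only known movers then turns a null HR of 1.00 into about 1.016. At 12%/8% with no movers known, it leaves 0.98 uncorrected. A sensitivity analysis that censors unreachable patients with no later INPC activity gave 0.998 to 1.004 in every case tried.

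**Randomisation factors.** 1,500 simulated trials per scenario, n = 194, about 38 events, true HR 0.75, assuming 50% aged 60+ and 25% men.

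| Assumed age/sex HR | Median HR, unadjusted | With covariates | Difference |
|---|---|---|---|
| 1.5/1.5 | 0.746 | 0.743 | 0.003 |
| 2/2 | 0.755 | 0.748 | 0.007 |
| 3/2 | 0.764 | 0.750 | 0.014 |

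The smallest of the four sex-by-age cells had a median of only 3 to 5 events, so covariates are safer than a stratified model.

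**The case against.** The strongest reply is that little observation will be lost. Section 1.0 stresses that INPC searches need no patient participation, and section 8.0 calls 10% conservative. That stands: patients who merely miss visits or calls are rightly followed to the end date, and the expected bias is small.

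A reader might infer that the plan definitely carries lost patients as event-free. It does not say so. Counting 194 completers for events, and promising supplemental completer analyses, leaves exclusion as a live reading. What can be said is that the handling is unspecified and that the literal rule has the effect shown.

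A reader might also infer a built-in bias towards eIMPACT. Ground (c) in section 7.0 applies when "the participant, in the assessment of the eIMPACT psychiatrist, exhibits evidence of a psychotic disorder or bipolar disorder", and in usual care "participants in this group do not receive any depression treatment from the study team", so the route appears to operate mainly in one arm. But nothing in the documents says that this discontinuation ends INPC ascertainment, so unequal loss is possible and not shown. Larger shifts need larger imbalances: 15% against 5% would turn a true 0.75 into about 0.71 or 0.79, depending on the arm, and no section supports such a gap.

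On the model, section 4.0 stratifies because sex and age correlate with FMD, the primary outcome, and not because of CVD events. The unadjusted Cox model is valid. The case for adjustment is consistency with the design at almost no cost.

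**Conclusion.** The point holds at low severity. Section 8.0 gives no censoring date for patients whose record access ends, and the plan foresees such patients. Under the literal rule, equal loss leaves the HR essentially unbiased and understates the event rate, by about one percentage point at 10% loss. Modest unequal loss shifts the HR by about 0.01 to 0.02. Omitting sex and age group changes the median HR by at most 0.014 under the assumed prognostic strengths. All loss splits, hazard shapes and covariate effects are assumptions. Each shift is small beside an interval of 0.40 to 1.40. The outcome is exploratory and power for it is disclaimed, and the FMD and mechanism hypotheses are untouched. The documents do not support a claim that the event analysis is invalid or that it is tilted towards eIMPACT.

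**What to change.** In section 8.0:

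1. Censor at the earliest of non-CVD death, the date record access is withdrawn, and the end date. State that patients who only miss calls remain under INPC observation to the end date. Report early ends of ascertainment by number, timing and arm.
2. Handle suspected movers only in a sensitivity analysis: censor patients who cannot be reached and have no later INPC activity at the later of their last INPC encounter or last call. Do not censor known movers alone in the main analysis, because that can itself bias the HR if knowledge differs by arm.
3. Include sex and age group (50-59, 60+) as covariates in the Cox model.
4. Report the HR with its 95% CI as descriptive, and note that with about 39 events an HR of 0.75 or less arises in about 18% of trials with no effect.

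The cost is SAP wording, one date per affected patient, two covariates, and one extra run on data already searched every 6 months. The sensitivity analysis may censor some patients who are still in coverage but had no encounters, so it should not replace the main rule. The sponsor also accepts a less favourable statement of what the event data can show.
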